8.3 Emergency unblinding of treatment assignment

Not applicable, this is an open-label study.

8.4 Pregnancies

To ensure patient safety, each pregnancy occurring while the patient is on study treatment must be reported to Novartis within 24 hours of learning of its occurrence and deferasirox must be discontinued. The pregnancy should be followed up to determine outcome, including spontaneous or voluntary termination, details of the birth, and the presence or absence of any birth defects, congenital abnormalities, or maternal and/or newborn complications.

Pregnancy should be recorded on a Clinical Trial Pregnancy Form and reported by the investigator to the oncology Novartis Chief Medical Office and Patient Safety (CMO&PS). Pregnancy follow-up should be recorded on the same form and should include an assessment of the possible relationship to the study treatment any pregnancy outcome. Any SAE experienced during pregnancy must be reported on the SAE Report Form.

8.5 Warnings and precautions

No evidence available at the time of the approval of this study protocol indicated that special warnings or precautions were appropriate, other than those noted in the provided IB. Additional safety information collected between IB updates will be communicated in the form of Investigator Notifications. This information will be included in the patient informed consent and should be discussed with the patient during the study as needed.

8.6 Data Monitoring Committee

Not applicable.

8.7 Steering Committee

Not applicable.

9 Data collection and management

9.1 Data confidentiality

Novartis

Information about study subjects will be kept confidential and managed under the applicable laws and regulations. Those regulations require a signed subject authorization informing the subject of the following:

- What protected health information (PHI) will be collected from subjects in this study
- Who will have access to that information and why
- Who will use or disclose that information
- The rights of a research subject to revoke their authorization for use of their PHI.

In the event that a subject revokes authorization to collect or use PHI, the investigator, by regulation, retains the ability to use all information collected prior to the revocation of subject authorization. For subjects that have revoked authorization to collect or use PHI, attempts should be made to obtain permission to collect follow-up safety information (e.g. has the subject experienced any new or worsened AEs) at the end of their scheduled study period.

The data collection system for this study uses built-in security features to encrypt all data for transmission in both directions, preventing unauthorized access to confidential participant information. Access to the system will be controlled by a sequence of individually assigned user identification codes and passwords, made available only to authorized personnel who have completed prerequisite training.

9.2 Site monitoring

Before study initiation, at a site initiation visit or at an investigator's meeting, Novartis personnel (or designated CRO) will review the protocol and eCRFs with the investigators and their staff. During the study, the field monitor will visit the site regularly to check the completeness of patient records, the accuracy of entries on the eCRFs, the adherence to the protocol to Good Clinical Practice, the progress of enrollment, and to ensure that study treatment is being stored, dispensed, and accounted for according to specifications. Key study personnel must be available to assist the field monitor during these visits.

The investigator must maintain source documents for each patient in the study, consisting of case and visit notes (hospital or clinic medical records) containing demographic and medical information, laboratory data, electrocardiograms, and the results of any other tests or assessments. All information recorded on eCRFs must be traceable to source documents in the patient's file. The investigator must also keep the original signed informed consent form (a signed copy is given to the patient).

The investigator must give the monitor access to all relevant source documents to confirm their consistency with the eCRF entries. Novartis monitoring standards require full verification for the presence of informed consent, adherence to the inclusion/exclusion criteria and documentation of SAEs. Additional checks of the consistency of the source data with the eCRFs are performed according to the study-specific monitoring plan.

Protocol No. CICL670AIC04

9.3 Data collection

For studies using Electronic Data Capture (EDC), the designated investigator staff will enter the data required by the protocol into the eCRF. The eCRFs have been built using fully validated secure web-enabled software that conforms to 21 CFR Part 11 requirements, Investigator site staff will not be given access to the EDC system until they have been trained. Automatic validation programs check for data discrepancies in the eCRFs and, allow modification or verification of the entered data by the investigator staff.

The Principal Investigator is responsible for assuring that the data entered into eCRF is complete, accurate, and that entry and updates are performed in a timely manner.

9.4 Database management and quality control

For studies using eCRFs, Novartis personnel (or designated CRO) will review the data entered by investigational staff for completeness and accuracy. Electronic data queries stating the nature of the problem and requesting clarification will be created for discrepancies and missing values and sent to the investigational site via the EDC system. Designated investigator site staff are required to respond promptly to queries and to make any necessary changes to the data.

Concomitant treatments and prior medications entered into the database will be coded using the WHO Drug Reference List, which employs the Anatomical Therapeutic Chemical classification system. Medical history/current medical conditions and adverse events will be coded using the Medical dictionary for regulatory activities (MedDRA) terminology.

At the conclusion of the study, the occurrence of any protocol violations will be determined. After this action has been completed and the data has been verified to be complete and accurate, the database will be declared locked. Authorization is required prior to making any database changes to locked data, by joint written agreement between the Head of Biostatistics, PLSS and Data Management and the Global Head of Clinical Development.

For EDC studies, after database lock, the investigator will receive a CD-ROM or paper copies of the patient data for archiving at the investigational site.

10 Statistical methods and data analysis

Data from all centers participating in this study will be pooled for analyses.

Standard descriptive analyses will include:

- Frequencies and percentages for categorical data;
- n, mean, standard deviation, minimum, median, 25th and 75th percentiles and maximum for continuous data.

Additional information for analysis methods will be available in statistical analysis plan documentation

10.1 Analysis sets

10.1.1 Full Analysis Set

The Full Analysis Set (FAS) comprises of all patients enrolled in this study.

10.1.2 Safety set

The Safety Set includes all enrolled patients who received at least one dose of study treatment (deferasirox FCT) and had at least one safety assessment on or after Visit 3 (Day 1).

An entry on the AE eCRF page of "no AE" constitutes as a safety assessment.

The safety analyses will be performed on the safety set and the efficacy (serum ferritin) on the on the FAS.

10.1.3 Other analysis sets

Not applicable.

10.2 Patient demographics/other baseline characteristics

Demographic and other baseline data will be summarized descriptively by formulation and overall for the FAS.

Demographic data included age, age group (< 18 years, 18-< 50 years, 50-< 65 years, \geq 65 years), gender, race, and ethnicity (Hispanic/Latino, Chinese, Indian (Indian subcontinent), Japanese, Other). Other background data included weight, weight group (< 20 kg, 20-< 35 kg, 35-< 55 kg, 55-< 75 kg, \geq 75 kg), height, main underlying disease, history of splenectomy (Yes/No), history of chelation therapy (Yes/No), prior deferasirox (Yes/No), type of last chelation therapy prior to the study, Hepatitis B and C status, medical history by MedDRA primary SOC and preferred term, clinically significant abnormality in ECG (Yes, No), overall interpretation in audiometric test (Normal, Clinically insignificant abnormality, Clinically significant abnormality), overall interpretation in ocular exam (Normal, Clinically insignificant abnormality, Clinically significant abnormality), baseline creatinine, baseline creatinine group (\leq ULN, > ULN), baseline creatinine clearance, baseline creatinine clearance group (\leq 00, 60- \langle 90, 90- \langle 160, \rangle 160 mL/min), baseline ALT/SGPT, baseline ALT/SGPT group (\leq ULN, \rangle ULN-5 \times ULN, \rangle 5 \times ULN), urine protein/creatinine ratio (\leq 0.2 mg/mg, \rangle 0.2- \leq 1 mg/mg, \rangle 1 mg/mg).

Categorical data will be presented as frequencies and percentages. For continuous data, mean, standard deviation, median, 25th and 75th percentiles, minimum, and maximum will be presented.

10.3 Treatments (study treatment, concomitant therapies, compliance)

The following variables will be summarized with descriptive measures for the Safety Set: duration of exposure (at intervals as described in the Statistical Analysis Plan); average planned (mg/kg/day) and average actual daily dose (mg/day); cumulative planned (mg/kg) and total actual dose (mg); percentage of planned dose taken; frequency of interruptions,

decreases and increases in planned dose overall and by reason for change as recorded in the eCRF.

The total patient-years while on treatment, calculated as the sum of (overall drug exposure)/365.25 will be provided.

The duration of exposure is defined as the number of weeks between the start and end of study medication. The end of study medication day is the last day with a non-zero actual dose of study medication as recorded on the drug administration pages.

The average daily dose (planned or actual) is calculated as the mean dose over all days between first and last dose, including interim days with zero dose (interruptions). The cumulative dose is calculated as the sum over the daily doses of all days between first and last dose. The current weight is used when calculating the actual daily dose.

The percentage of planned dose taken is derived as $100 \times \text{cumulative}$ actual dose (mg)/cumulative planned dose (mg/kg).

Prior and concomitant medications and significant non-drug therapies will be summarized using frequency tables according to WHO Anatomical Therapeutic and Chemical class and WHO generic term. Prior medications are defined as drugs taken prior to the first dose of study medication. Concomitant medications are medications taken between the first and last day with study medication, excluding medications started on the last day of study medication. Medications which start prior to the first dose of study medication and continue thereafter are counted in both summaries.

10.4 Primary objective

The primary objective of this study is to evaluate the overall safety of the deferasirox FCT formulation, as measured by frequency and severity of AEs and changes in laboratory parameters, in patients with transfusion-dependent thalassemia or MDS at very low, low or intermediate risk.

10.4.1 Variable

The primary objective of this study is safety. The safety set will be used for the analysis of safety parameters.

The overall observation period in this study will be divided into 3 mutually exclusive segments:

- 1. Pre-treatment period: from day of patient's informed consent to the day before first dose of study medication
- 2. On-treatment period i.e. from day of first dose of study medication to 30 days after last dose of study medication
- 3. Follow-up period i.e. starting at day 31 after last dose of study medication

Any AEs during on-treatment period and changes from Baseline over time during on-treatment period for serum creatinine, creatinine clearance, ALT/SGPT, AST/SGOT, RBC, platelets and white blood cell will be analyzed.

10.4.2 Statistical hypothesis, model, and method of analysis

Descriptive statistical analyses will be performed to summarize the primary endpoints and include:

- Frequencies, percentages, and 95% confidence intervals (CIs) for overall incidences of any AEs during the on-treatment period.
- Number (n), mean, standard deviation, minimum, lower quartile, median, upper quartile and maximum time to AE.
- Number (n), mean, standard deviation, minimum, lower quartile, median, upper quartile and maximum for laboratory values for selected laboratory parameters at Baseline, and after Months 6 and 12.
- Mean \pm SE plots for laboratory values for selected laboratory parameters at Baseline, and after Months 6 and 12.

For all analysis purposes Baseline refers to the Day 1 (Visit 3) of the current study.

10.4.3 Handling of missing values/censoring/discontinuations

No missing data will be imputed.

10.4.4 Supportive and Sensitivity analyses

Overall AEs and selected laboratory parameters (serum creatinine and creatinine clearance) of the primary objective will be analyzed for the following subgroups: Main underlying diseases (MDS and Beta-thalassemia), age groups (10-< 18, 18-< 65 and \geq 65 years), actual average daily dose categories (< 7 mg/kg/day, 7-21 mg/kg/day, and \geq 21 mg/kg/day) and prior chelation therapy (DFX, any other ICT).

10.5 Secondary objectives

10.5.1 Secondary efficacy objective

To evaluate efficacy of deferasirox FCT on serum ferritin levels (decrease or maintenance, according to the individual therapeutic goal)

Serum ferritin level will be summarized at Baseline and at Months 6 and 12 and change from Baseline for the FAS.

The Baseline serum ferritin value will be defined as the average of the 2 measurements obtained during the Screening period.

The absolute and relative change with 95% CI from Baseline at Months 6 and 12 will be calculated.

10.5.2 Other Safety objectives

All safety analyses described below will be based on the safety set.

10.5.2.1 Adverse events (AEs)

Summary tables for AEs have to include only AEs that started or worsened during the ontreatment period, the *treatment-emergent* AEs. However, all safety data (including those from the pre and post-treatment periods) will be listed and those collected during the pre-treatment and post-treatment period are to be flagged.

The incidence of treatment-emergent AEs (new or worsening from Baseline) will be summarized by system organ class and or preferred term, severity, type of AE, relation to study treatment and AEs requiring dose adjustment or interruption. Exposure-adjusted AE incidence defined as the number of patients with new or worsened AEs during period/[total number of days patient was on treatment summed for all patients/365.25 days] will be presented.

An overall summary of type of AEs (e.g. serious, leading to study drug discontinuation, requiring dose adjustment or/and interruption) will be presented by severity.

Specific groupings of AEs of special interest will be considered and the number of patients with at least one event in each grouping will be reported. Such groups consist of AEs for which there is a specific clinical interest in connection with Deferasirox treatment or adverse events which are similar in nature (although not identical). Note that certain AEs may be reported within multiple groupings/AEs of special interest.

AEs of special interest are defined by MedDRA terms. Definition for retrieval and maintenance is done in separate document in the Novartis Documentum management system at the path "CREDI Projects/I/ICL670A/Integrated Medical Safety". The latest document has to be used.

Incidence of AEs of special interest will be summarized by grouping and preferred term.

10.5.2.2 Laboratory abnormalities

All laboratory values will be converted into SI units and the severity grade calculated using the low/normal/high classifications based on laboratory normal ranges, and for selected parameters by notable/extended ranges (see Table 10-1 below).

The following summaries will be generated separately for hematology, biochemistry and urinary laboratory tests:

- shift tables using normal/notable/extended ranges to compare Baseline to the worst on-treatment value
- listing of all laboratory data with values flagged to show the corresponding normal/notable/extended ranges

Laboratory values (and changes from Baseline) will be summarized by descriptive statistics (n, mean, standard deviation, minimum, lower quartile, median, upper quartile and maximum) by scheduled visits.

Table 10-1 Definition of notable/extended ranges for laboratory tests

Laboratory test

Criteria for notable ranges

Novartis	Confidential	Page 58
Amended Protocol Version 01 (Clean)		Protocol No. CICL 670AIC04

Laboratory test	Criteria for notable ranges
Platelet count	< 100 × 10 ⁹ /L (extended range < 50 × 10 ⁹ /L)
Absolute neutrophils	$< 1.5 \times 10^{9}$ /L (extended range $< 0.5 \times 10^{9}$ /L)
Serum creatinine	> 33% increase from Baseline and > ULN at 2 consecutive measurements at least 7 days apart
Creatinine clearance	< 60 mL/min at 2 consecutive measurements at least 7 days apart (extended range < 40 mL/min at 2 consecutive measurements at least 7 days apart)
Urinary protein/urinary creatinine ratio	> 1.0 (mg/mg) at 2 consecutive measurements at least 7 days apart
ALT/SGPT and AST/ SGOT	> 5 × ULN and 2 × Baseline (extended range > 10 × ULN and > 2 × Baseline value)

ULN = Upper limit of normal range; ALT/SGPT = alanine aminotransferase/ serum glutamic pyruvic transaminase; AST/SGOT = Aspartate aminotransferase/serum glutamic oxaloacetic transaminase

Creatinine clearance will be estimated using the Cockcroft-Gault equation and the Schwartz formula (for pediatric population) and will be displayed using relative change from baseline by categories.

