2.3.2 Baseline and post-baseline definitions

The baseline value for efficacy and safety variables is the last available, non-missing, (scheduled or unscheduled) value collected prior to first administration of study treatment on Day 1 of this study (or the first date when a non-zero actual dose of study drug was administered), unless otherwise stated.

Some baseline assessments may be recorded on the day of the baseline visit (Visit 3/Day 1). However the time of each of these assessments may not be recorded in the eCRF. In this case, only the assessments which, according to the protocol, should have been conducted pre-dose on Day 1 will be assumed to have been done prior to administration of study treatment on Day 1 when deriving baseline values recorded on the day of the baseline visit (Visit 3/Day 1).

All data collected after baseline (see Section 2.3.1 for definition of baseline date) are defined as post-baseline.

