2.3.3.2 Laboratory data and vital signs

Laboratory data (biochemistry, hematology, and urinary parameters as well as serum creatinine, creatinine clearance, and proteinuria) and vital signs will be collected at screening visits, regular patient visits, and EOT.

If two or more assessments are performed within a time window then the assessment closest to the planned visit will be used in analyses by time window. When two values are equidistant from the planned assessment, the later one will be used in analyses.

Note: For worst post-baseline assessment, all on-treatment values are considered regardless of time windows. Table 2-2 shows the defined time windows, where a month is regarded as 4 weeks.

Table 2-2 Time windows for laboratory and vital signs data

Time window	Planned visit timing	Time window definition
On-treatment		
Baseline	On or before Study Day 1*	≤ Study Day 1*
Week 2	Study Day 15	Study Day 2 to Study Day 21
Month 1	Study Day 29	Study Day 22 to Study Day 43
Month 2	Study Day 57	Study Day 44 to Study Day 71
Month 3	Study Day 85	Study Day 72 to Study Day 99
Month 4	Study Day 113	Study Day 100 to Study Day 127
Month 5	Study Day 141	Study Day 128 to Study Day 155
Month 6	Study Day 169	Study Day 156 to Study Day 183
Month 7	Study Day 197	Study Day 184 to Study Day 211
Month 8	Study Day 225	Study Day 212 to Study Day 239
Month 9	Study Day 253	Study Day 240 to Study Day 267

Time window	Planned visit timing	Time window definition
Month 10	Study Day 281	Study Day 268 to Study Day 295
Month 11	Study Day 309	Study Day 296 to Study Day 323
Month 12	Study Day 337	Study Day 324 to Study Day 351
Month 13	Study Day 365	Study Day 352 to Study Day 379
Month 14	Study Day 393	Study Day 380 to Study Day 407
Month 15	Study Day 421	Study Day 408 to Study Day 435
Month 16	Study Day 449	Study Day 436 to Study Day 463
Month 17	Study Day 477	Study Day 464 to Study Day 491
Month 18	Study Day 505	Study Day 492 to Study Day 519
Month 19	Study Day 533	Study Day 520 to Study Day 547
Month 20	Study Day 561	Study Day 548 to Study Day 575
Month 21	Study Day 589	Study Day 576 to Study Day 603
Month 22	Study Day 617	Study Day 604 to Study Day 631
Month 23	Study Day 645	Study Day 632 to Study Day 659
Month 24	Study Day 673	Study Day 660 to Study Day 687
Month 25	Study Day 701	Study Day 688 to Study Day 715
Month 26	Study Day 729	Study Day 716 to Study Day 743
Month 27	Study Day 757	Study Day 744 to Study Day 771
Month 28	Study Day 785	≥ Study Day 772
EOT		

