2.9.3 Laboratory data

Hematology, serum chemistry, and urinalysis parameters will be presented using standard international (SI) units and the severity grade calculated using the low/normal/high classifications based on laboratory normal ranges, and for selected parameters by notable/extended ranges.

Raw values as well as absolute and relative change from baseline values for hematology, biochemistry, and urinalysis laboratory parameters will be summarized descriptively by visit (see Table 2-2 for time windows definition).

The following summaries will be generated separately for hematology, biochemistry, and urinary laboratory tests:

- shift tables using normal/notable/extended ranges to compare baseline to the worst ontreatment value
- listing of all laboratory data with values flagged to show the corresponding normal/notable/extended ranges

All data, including data from unscheduled visits, will be considered when identifying abnormal values.

Shift tables based on normal ranges to compare baseline to the worst post-baseline value will be provided by parameter for hematology, biochemistry, and urinary laboratory data.

A similar shift table will be provided based on notable/extended ranges for key safety laboratory parameters defined in Section 10.5.2.2 (Clinical Trial Protocol CICL670AIC04 Amended Protocol Version 1, 25 October 2017).

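### The notable/extended shift table is built on the single worst on-treatment value, while Table 10-1 defines the renal categories by two consecutive values, and neither document links the two rules

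*Protocol*

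**What the plan says.** Protocol section 10.5.2.2 asks for "shift tables using normal/notable/extended ranges to compare Baseline to the worst on-treatment value". Table 10-1, in the same section, gives the ranges. Three of them are renal and contain a confirmation condition:

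- For clearance the notable range is "< 60 mL/min at 2 consecutive measurements at least 7 days apart", and the extended range, below 40 mL/min, carries the same two-measurement condition.
- For the urine protein/creatinine ratio it is "> 1.0 (mg/mg) at 2 consecutive measurements at least 7 days apart".
- For creatinine in serum it is relative to the patient's own starting value: "> 33% increase from Baseline and > ULN at 2 consecutive measurements at least 7 days apart".

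SAP section 2.9.3 carries the table over as "shift tables using normal/notable/extended ranges to compare baseline to the worst ontreatment value". After describing the normal-range shift tables it adds: "A similar shift table will be provided based on notable/extended ranges for key safety laboratory parameters defined in Section 10.5.2.2". It also says that unscheduled data count when abnormal values are identified. SAP section 2.3.3.2 states: "For worst post-baseline assessment, all on-treatment values are considered regardless of time windows".

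For baseline, SAP section 2.3.2 uses one value, which "is the last available, non-missing, (scheduled or unscheduled) value collected prior to first administration of study treatment". SAP section 2.4.2 groups baseline clearance as below 40, 40 to below 60, and 60 mL/min or more, with no two-measurement condition. The SAP document history says these groups were chosen to match the shift table categories.

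**The concern.** A single worst value cannot show whether a two-measurement criterion was met. Two programmers working from the same text could therefore produce different tables from the same data. One would classify the minimum clearance (or the maximum creatinine or urine ratio). The other would search the series for confirmed pairs.

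The choice matters most for creatinine and clearance, because Protocol Table 3-1 names them as the laboratory values of interest for the primary safety objective. Each patient can contribute up to 25 scheduled post-baseline values plus unscheduled ones, so a rule that reacts to any one value will pick up measurement variation. There is no control arm to show how often that happens. The planned maximum is 58 patients (SAP section 3), so each reclassified patient moves a percentage by 1/58 = 1.7 points.

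**Working it through.** The plan states no event rate or sample size calculation for this table, so there is no figure to reproduce. The check has three parts.

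**1. The two rules applied to the same clearance series (mL/min)**

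| Series | Single worst value | Two consecutive values (Table 10-1) |
|---|---|---|
| 72, 58, 71 | 58: notable | no pair below 60: not notable |
| 55, 38, 57 | 38: extended | pairs below 60 but none below 40: notable only |
| 58, 59, 70 | 58: notable | 58 and 59 both below 60: notable |

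The rules agree when the abnormality persists and disagree when it is isolated.

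**2. The baseline row**

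- Serum creatinine: the change of Baseline from itself is 0%, so an increase above 33% cannot occur at baseline. A baseline notable row is empty by arithmetic.
- Clearance: one value cannot meet a two-value rule read literally, but the SAP 2.4.2 groups can fill the row from one value.
- Urine ratio: SAP 2.4.2 has a group above 1.0 mg/mg, so the same applies. Few patients should fall there, because Protocol section 5.3 excludes a ratio above 0.5 mg/mg at either screening visit.

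**3. How far the rules can diverge for clearance**

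Inputs:
- Number of values: Visits 4 to 28, so 28 − 4 + 1 = 25 (Protocol Table 7-1 and section 7.1.3).
- Cut-off: 60 mL/min (Table 10-1).
- Assumptions not given in the documents: constant true clearance μ, normally distributed values, within-patient CV 10%, independent visits, all 25 visits attended.

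Formulas:
- Chance that one value is below 60: p = Φ((60 − μ)/(0.10 μ)).
- Chance of at least one value below 60: 1 − (1 − p)^25.
- Chance of two consecutive values below 60: exact recursion over 25 visits. Let a be the chance of no pair yet with the last value not low, b the chance of no pair yet with the last value low, and h the chance that a pair has occurred. Start at a = 1, b = h = 0. At each visit a becomes (a + b)(1 − p), b becomes a·p, and h becomes h + b·p, all from the previous visit's values.

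Example at μ = 75: (60 − 75)/7.5 = −2, so p = 0.0228. Any low value: 1 − 0.9772^25 = 0.44. Pair: 0.012; the rough check 24p² = 0.0124 agrees.

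| True clearance | p | Any value below 60 | Two consecutive below 60 |
|---|---|---|---|
| 70 | 0.0766 | 86% | 12% |
| 75 | 0.0228 | 44% | 1.2% |
| 80 | 0.0062 | 14% | 0.1% |
| 90 | 0.0004 | 1% | 0% |
| 100 | 0.00003 | 0.1% | 0% |

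Sensitivity:
- CV at a true clearance of 75: 8% gives about 14% against 0.1%; 12% gives 71% against 5%.
- CV 15% at a true clearance of 90: 28% against 0.4%.
- Correlation at a true clearance of 75 and CV 10% (simulated): lag-1 correlation 0.4 gives 39 to 40% against 6%; 0.7 gives about 30% against 11%. Correlation lowers the first figure and raises the second, so the gap narrows but does not close.

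**The case against.** The strongest reply is that the confirmation condition was never removed. Both documents take the notable and extended ranges from Protocol 10.5.2.2, so the condition comes with them, and worst value can be read as worst category met. SAP 2.3.3.2 only lifts the one-value-per-window selection. Including unscheduled data is compatible with searching the whole series for pairs. The table shells, which the SAP mentions but which are not available here, may specify the derivation.

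This stands in part. A confirmed reading is possible, and a reader who inferred that the plan explicitly drops confirmation would be going further than the text. But the only clearance categories that the SAP says were aligned with the shift table are unconfirmed single-value groups, which points the other way. A literal programmer would have text to support an unconfirmed table.

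A reader might also infer that the baseline row can never be filled for any of the three parameters. That is strict only for serum creatinine. The SAP 2.4.2 groups serve clearance and the urine ratio, and a baseline clearance below 60 would then appear in its own row and not as a new shift. An empty creatinine row misclassifies nobody.

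Finally, it is fair to say that the consequence is limited. The normal-range shift tables, the display of clearance by relative change, the adverse event summaries and the Month 6 and 12 changes from baseline do not depend on this rule. The cells are shift categories, not renal events, and no hypothesis is tested. The full data listing lets a reader trace individual values, although its notable/extended flags need the same clarification.

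**Conclusion.** The mismatch is real and should be resolved before the table is programmed. As written, the plan permits an isolated value to be shown as notable or extended although Table 10-1 requires confirmation, and the SAP leans towards that reading. Confirmation is the protocol's own concept: its creatinine monitoring text in section 6.3.1.2 also refers to two consecutive visits.

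The size cannot be predicted from the documents, because they give neither the within-patient variability nor the distribution of baseline clearance. For patients with a true clearance of 70 to 75 mL/min the two rules can differ by tens of percentage points. At 90 or more with a CV of 10% they differ by about one point or less. The 44% and 86% figures describe patients near the cut-off under independence and full attendance; they should not be read as expected rates for the study. Nor do the documents support reading this as a flaw in the primary analysis. It concerns one descriptive safety table.

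**What to change.** In SAP section 2.9.3:

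1. For serum creatinine, creatinine clearance and urine protein/creatinine ratio, define the on-treatment category as the worst category confirmed under Table 10-1. Use all on-treatment values, including unscheduled ones, and state how values less than 7 days apart are handled.
2. Count a last abnormal value with no later measurement separately, as unconfirmed.
3. For the baseline row, keep the single SAP 2.3.2 value, with the SAP 2.4.2 cut-offs for clearance and the one baseline value for the urine ratio. Add a footnote that baseline is unconfirmed. Building a confirmed baseline from the two screening visits is not advised: it departs from SAP 2.3.2 and from the Visit 3 baseline in Protocol 10.4.2, and the two values may span the 5-day washout.
4. Report the serum creatinine criterion as patient counts and percentages, with no baseline row.
5. If a single-worst-value notable table is also kept, label it unconfirmed.

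The cost is a few lines of SAP text and one changed derivation. No new data are needed, because all three parameters are scheduled at every treatment visit.
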